Profile of Mood States Abbreviated [21]. Participants are presented with a list of 40 words that describe feelings people have. They are asked to circle the number that best describes how they feel right now from 0 (not at all), 1 (a little), 2 (moderately), 3 (quite a lot) to 4 (extremely). Alogue scales - . A Total Mood Disturbance score (TMD) is also calculated by summing the totals for the negative subscales (Tension, Depression, Anger, Fatigue, Confusion), and subtracting the totals for the positive scales (Vigour, Esteem-related Affect [Note that 2 item are reverse scored for the ERA subscale]). See Appendix 3. The primary outcome measure is the TMD, but we will conduct secondary analyses to examine the effects of the interventions on the subscale scores.

Modified Auckland Sleep Questionnaire [22]. The Auckland Sleep questionnaire was developed to diagnose common sleep disorders in primary care. We will use the items about current sleep and asked participants to rate them in reference to the previous week (rather than the previous month as in the original questionnaire). The overall sleep quality rating will be used in the analysis (Appendix 4).

Visual Analogue Scales

To assess the acute effects of the intervention, participants will be asked to complete ratings of overall mood, relaxation, and stress before and after one session each week. Participants are asked to rate how they are feeling *right now* using a visual analogue scale (VAS) from 0 (worst I've ever felt not relaxed, not stressed,) to 100 (very stressed, very relaxed, best I've ever felt)[23, 24] see Appendix 5.

e) Objectives

Primary Objective

To determine if the effects of listening to singing bowl music are equivalent to that of progressive guided muscle relaxation on self-report measures of mood in young adults (Total Mood Disturbance of the POMS) at 4- and 8- weeks post intervention.

Secondary Objectives

To compare the effects of the interventions on:

- Profile of Mood States-Abbreviated (POMS) subscale scores
- Overall sleep quality from the Auckland Sleep Questionnaire
- VAS ratings of mood, stress and relaxation

Exploratory analyses will be undertaken to determine i) how frequently the participants use the interventions in weeks 4-8, and ii) the acceptability of the interventions.

4. Study population

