Members of the general population aged 16-25 years will be recruited to participate in the study. To be eligible to take part, potential participants need to have good hearing, good understanding of English and have a mobile phone or computer to access the intervention and questionnaires via the Qualtrics application. Participants will be excluded if: they are regular users of relaxation music from quartz crystal singing bowls or progressive muscle relaxation, have an untreated mental health diagnosis, or are receiving treatment from a psychologist or psychiatrist. (See Appendix 1 for the eligibility questionnaire).

Participants will initially be recruited from the first-year psychology participant research pool (IPRP) and will receive up to 10% course credit for participation (as outlined in the flyer and participant information sheet (PIS) appendices 7 and 8. Study flyers will also be posted around the University to recruit more widely (participants can choose to enter a prize draw). In the next stage of the study, we will approach secondary schools to advertise the research to their students (subject to additional ethics approval).

We aim to recruit at least 100 participants, with a minimum of 50 university students.

5. Study Procedures

The study/questionnaires will be delivered via the Qualtrics software. Those interested in participating will contact the researchers via a study email address [contact]. Each participant will be allocated to one of the students who will be responsible for monitoring the participant's completion of the questionnaires and sending reminders to complete the intervention as needed. Participants will be sent an individual link to the information sheet, consent form, and eligibility form (Appendices 1, 8). Those meeting the eligibility criteria will automatically be directed to complete the demographic questionnaire (Appendix 2), and the mood (POMS) and sleep measures (modified Auckland Sleep questionnaire) Appendix 3 & 4, (T1).

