Participants will then be randomised to either the singing bowl (SB) (Tranquility by [name]) or the guided relaxation group (PMR; example script is in Appendix 6) and given access to the relevant audio on the qualtrics platform (to allow us to monitor when and for how long participants engaged with the intervention). Participants will be asked to listen to the relevant intervention 3 times a week for four weeks (each session is approximately 10 minutes). Before and after one session each week, participants will be asked to complete the visual analogue ratings scales to assess the acute effects of the intervention on their mood, stress and relaxation (Appendix 5). Participants will be sent reminders 3 x per week to complete the intervention.

Participants will be asked to complete the mood and sleep measures again after 4- (T2) and 8-weeks (T3)

The students will actively monitor participant's engagement in the study and send email reminders to complete the intervention sessions (Qualtrics is set up to automatically send email notifications to the study email address when participants complete each session so we can keep track of where they are up to) and the questionnaires at 4 and 8 weeks after the start of the study. After the first four weeks, participants will have free access to either the SB or PMR audio to use as much as they like, and we will monitor the frequency of use via the qualtrics app for the next four weeks. We will send out the link to the intervention weekly in weeks 4-8.

After completion of the 8 week questionnaire (T3) participants will be provided unlimited (and unmonitored) access to both audio tracks and will be asked to provide any feedback on the study.

6. Statistical Analysis

Primary outcomes

Difference scores between baseline (T1) and T2 (4 weeks), and T3 (8 weeks) for the POMS TMD will be calculated.

Secondary outcomes

- a) Difference scores between baseline (T1) and T2 (4 weeks), and T3 (8 weeks) for the POMS subscale scores and Auckland Sleep questionnaire will be calculated.
- b) The number of intervention sessions completed between T1 and T2, and T2 and T3.
- c) Feedback on the acceptability and effectiveness of each intervention.

Sample size

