A previous study examining the effects of an in person Tibetan singing bowl (n=62) session showed mean reductions of 0.49 to 1.23 (SD 0.19-1.05) in five POMS subscale scores [16]. A study with a much smaller group of teenage males (n= 11) showed significant reductions in POMS depression scores post-intervention [19]. In person PMR or Autogenic relaxation sessions in young soccer players (n=8) produced significant reductions in four of the six POMS-A subscales (mean difference 2.13 to 4.25; SD 2.38 to 4.47) [25]. As the current study is online rather than in-person, and the sessions are shorter, the effects may be somewhat smaller. Given this we are aiming to recruit a minimum of 100 participants (50 per group). This will provide > 90% power (2-sided $\alpha=0.05$) to detect a medium size effect of the intervention on the POMS subscales.

Analysis Plan

Univariate repeated measures ANOVA will be used to examine the effects of the intervention on the overall TMD score from the POMS, VAS scores and sleep scores. Repeated measures MANOVA will be used to examine changes in the POMS subscale scores.

Participants will be excluded from the analyses if they have not completed at least one intervention session per week for the first four weeks. The number of sessions completed during the first four weeks may be included as a covariate in the analyses.

7. Safety Concerns

Participants will be encouraged to contact us if they have any concerns. We will discuss the issue with the clinical advisor (with the participants consent) and encourage the participants seek support from their GP in the first instance. We will also have a list of support organisations available for participants.

8. Publication

All listed investigators will be co-authors on any presentation or manuscript published from this study. The principal investigators will be the first authors on the study manuscript.

9. References

1. Health Mo. Annual Data Explorer 2022/23: New Zealand Health Survey [Data File]. 2023.

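### Baseline TMD, measured before randomisation, is not used as a covariate in the primary analysis; adjusting for it would generally give a more precise arm difference at almost no cost

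*Combined protocol and SAP*

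**What the plan says.** Section 5 (Study Procedures) has eligible participants complete the POMS and sleep measures at T1. The next step reads "Participants will then be randomised to either the singing bowl (SB") or guided relaxation, so T1 is a true pre-randomisation baseline. The same measures are repeated at 4 weeks (T2) and 8 weeks (T3).

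Section 6, Primary outcomes: "Difference scores between baseline (T1) and T2 (4 weeks), and T3 (8 weeks) for the POMS TMD will be calculated".

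Section 6, Analysis Plan: "Univariate repeated measures ANOVA will be used to examine the effects of the intervention on the overall TMD score from the POMS". It does not say whether the difference scores or the T1, T2 and T3 scores enter that ANOVA, and it names no method for missing follow-up.

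The only covariate mentioned is optional and measured after randomisation: "The number of sessions completed during the first four weeks may be included as a covariate in the analyses". Baseline TMD is not named as a covariate anywhere in Section 6.

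The primary objective (Section 3e) is "To determine if the effects of listening to singing bowl music are equivalent to that of progressive guided muscle relaxation" on TMD at 4 and 8 weeks.

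**The concern.** A difference score fixes the weight on baseline at 1. Covariate adjustment estimates that weight from the data, and for a measure that is only moderately stable over 4 to 8 weeks the best weight is usually below 1. Subtracting the whole baseline then adds noise to the arm comparison.

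The weight-of-1 description applies to difference scores. If T1, T2 and T3 enter one ANOVA and the group main effect is read, the problem is different. T1 is averaged in with the follow-ups, although the arms cannot differ there except by chance, so the estimated arm effect shrinks.

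An equivalence objective is judged by whether a confidence interval is narrow enough to lie inside a margin. An interval wider than the collected data allow works directly against it.

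**Working it through.** **Inputs.** From the documents: 50 per group, two-sided alpha 0.05 (Section 6, Sample size); T1 before randomisation; T2 and T3 follow-up. Assumed, because the documents give no values: the baseline-to-follow-up correlation rho, and k = follow-up SD / baseline SD. The baseline SD is set to 1.

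**The plan's own figure.** Section 6 states power above 90% for a medium effect on the POMS subscales, not on TMD, and does not define medium. Taking it as 0.5 SD, a two-group comparison with 50 per group gives 69.7% (t-based). A within-group paired test with n = 50 gives 93.4%, and a group-by-time convention with f = 0.25 and N = 100 gives 93.8% or more. The text does not say which was meant, and nothing below depends on it.

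**Step 1: one follow-up visit.**
- Var(change) = 1 + k² − 2·rho·k
- Var(adjusted) = k²·(1 − rho²)
- CI narrowing = 1 − √(Var(adjusted)/Var(change))

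Example, k = 1 and rho = 0.5: Var(change) = 1.00, Var(adjusted) = 0.75, and 1 − √0.75 = 13.4%.

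Estimating the slope inflates the adjusted variance by about 97/96 (1%) and uses one degree of freedom (t critical value 1.9845 becomes 1.9847). In the example, 1 − √(0.75 × 97/96) = 12.9%.

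| k | | rho 0.3 | 0.5 | 0.7 | 0.8 |
|---|---|---|---|---|---|
| 1 | variance ratio | 0.650 | 0.750 | 0.850 | 0.900 |
| 1 | narrowing, formula | 19.4% | 13.4% | 7.8% | 5.1% |
| 1 | narrowing, slope estimated | 19.0% | 12.9% | 7.3% | 4.6% |
| 1.25 | variance ratio | 0.784 | 0.893 | 0.981 | 1.000 |
| 1.25 | narrowing, formula | 11.4% | 5.5% | 1.0% | 0.0% |
| 1.25 | narrowing, slope estimated | 11.0% | 5.0% | 0.4% | −0.5% |
| 0.8 | variance ratio | 0.502 | 0.571 | 0.628 | 0.640 |
| 0.8 | narrowing, formula | 29.1% | 24.4% | 20.8% | 20.0% |
| 0.8 | narrowing, slope estimated | 28.8% | 24.0% | 20.4% | 19.6% |

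The gain vanishes when the baseline slope rho·k reaches 1, as at k = 1.25 and rho = 0.8. A simulation at 50 per group (10,000 runs) agrees with the slope-estimated rows to within about 0.2 percentage points.

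**Step 2: illustration as superiority power.** For a true difference of 0.5 SD, k = 1, 50 per group, noncentral t, with the 97/96 inflation charged to the adjusted analysis:

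| | rho 0.3 | 0.5 | 0.7 | 0.8 |
|---|---|---|---|---|
| change score | 55% | 70% | 89% | 97.5% |
| adjusted | 73% | 81% | 93% | 98% |

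This is power to detect a difference. Equivalence power cannot be computed, because no margin is given.

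**Step 3: T1 as a time level.** Assume equal correlations among the three visits, equal SDs, and a 0.5 SD effect at both T2 and T3. Averaging over three visits cuts the effect to (0 + 0.5 + 0.5)/3 = 0.333 SD, with variance (1 + 2·rho)/3. Adjusting the T2/T3 mean for T1 keeps 0.5 SD, with variance (1 + rho)/2 − rho². Superiority power at rho 0.3, 0.5 and 0.7:
- group main effect over T1–T3: 62, 52, 45%
- two-degree-of-freedom group-by-time test: 57, 73, 92%
- adjusted T2/T3 mean: 91, 94, 98% (slope inflation included)

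**Step 4: participants with one follow-up.** A classical ANOVA on T1–T3 drops anyone missing either follow-up; a mixed model keeps those with one. If a fraction p is missing at each visit, the share with exactly one follow-up lies between 0 (the same people miss both) and 2p (no overlap). For p = 5, 15 and 25% the ceiling is 10, 30 and 50%, and the expected share under independence, 2p(1 − p), is 9.5, 25.5 and 37.5%. The documents give no p.

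**The case against.** The strongest reply is that the planned change-score comparison is valid as it stands and that the benefit cannot be sized from the documents. Across the assumptions above it runs from a 29% narrower interval to one 0.5% wider. Both statements are correct and limit the weight of the point. They do not reverse it: the worst case is negligible and the rest of the range favours adjustment.

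A reader might infer several stronger things that the documents do not support:

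- **That omitting baseline adjustment biases the result.** It does not for change scores, because T1 precedes randomisation. The rule "Participants will be excluded from the analyses if they have not completed at least one intervention session per week for the first four weeks" can introduce bias, but that is a separate matter which baseline adjustment neither causes nor cures.
- **That the trial is shown to be underpowered for its primary objective.** The power figures concern superiority. With no margin, it cannot be shown that a narrower interval would change the equivalence conclusion.
- **That participants with one follow-up will be lost.** This happens only if T1–T3 enter one classical ANOVA. Difference scores analysed visit by visit would keep them. Nor does the adherence rule make such cases rare: someone who meets it and then leaves during the free-access weeks has T2 without T3.

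It is also fair to say that a mixed model goes further than the precision point requires. ANCOVA at each visit would secure the same gain.

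**Conclusion.** The point holds as an efficiency recommendation of unknown size. That adjustment is generally at least as precise is standard and reproduces. How much more precise depends on an undocumented correlation and SD ratio, and the single-visit figures rest on those assumptions.

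The POMS asks how participants feel at that moment, and the repeats are 4 and 8 weeks later, so a modest correlation is plausible; that is where adjustment helps most. This is an inference, not a documented value.

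The plan should change because the baseline is already collected, the objective depends on interval width, and the Analysis Plan leaves open a reading (T1 as a time level, group main effect) under which the arm effect is diluted. It is a should-fix matter and does not invalidate the planned change-score comparison.

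**What to change.** Before outcome data are seen, specify that T2 and T3 TMD are the outcomes and T1 TMD is a covariate, and report the adjusted arm difference with its confidence interval at week 4 and at week 8. Either form will do:

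- ANCOVA at each visit, with arm and baseline TMD; or
- a linear mixed model with arm, visit, arm × visit, baseline TMD and baseline × visit as fixed effects and an unstructured within-person covariance. This also keeps everyone in the analysis set with at least one follow-up, under a stated missing-at-random assumption.

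Either choice settles which scores enter the model. The cost is SAP wording, a routine procedure and about one degree of freedom per visit, with a negligible loss of precision if the baseline slope is near 1. No extra data, visits or participants are needed. The equivalence margin, the adherence exclusion and the subscale MANOVA are separate matters that this change does not resolve.

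### As written, the weekly-session exclusion also covers the session-count outcome, so use would be reported only in people selected on their use

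*Combined protocol and SAP*

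**What the plan says.** - Section 6, Secondary outcomes, item (b): "The number of intervention sessions completed between T1 and T2, and T2 and T3". No analysis set and no method is given for it.
- Section 6, Analysis Plan, after the ANOVA and MANOVA for TMD, VAS, sleep and POMS subscales: "Participants will be excluded from the analyses if they have not completed at least one intervention session per week for the first four weeks". The next sentence adds: "The number of sessions completed during the first four weeks may be included as a covariate in the analyses".
- Section 3e lists as exploratory "how frequently the participants use the interventions in weeks 4-8". The same T2-T3 use is a secondary outcome in section 6.
- Section 5 sets the requested amount: "Participants will be asked to listen to the relevant intervention 3 times a week for four weeks". For the second period there is no requested amount: "After the first four weeks, participants will have free access to either the SB or PMR audio to use as much as they like".
- Section 5 also describes the logging: "Qualtrics is set up to automatically send email notifications to the study email address when participants complete each session". Counts therefore exist for people who stop early.

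The plan defines no all-randomised set and does not promise the number excluded by arm.

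**The concern.** The exclusion is defined by session completion, and session completion is itself an outcome. If the rule is applied to that outcome, the people with the most informative low counts are dropped, although their counts are known. The reported figure then describes use among those who kept going, not uptake among those offered the audio. If one audio loses more people than the other before week 4, the session count will not show it, and nothing else in the plan commits to showing it. Adding an as-randomised analysis of TMD would not repair this, because the use outcome would still be taken from the selected group.

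**Working it through.** The plan contains no figure for use to reproduce. Its one computed figure is the power for the POMS subscales, which has no bearing here.

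**1. What follows from the text alone.** Requested sessions in T1-T2: 3 per week × 4 weeks = 12. The rule requires at least 1 in each of 4 weeks, so the minimum retained count is 4 × 1 = 4. Enumerating every pattern of 0 to 3 sessions per week over four weeks:
- retained participants score 4 to 12;
- excluded participants score 0 to 9.

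The rule acts on the weekly pattern, not the total. Someone with sessions 3, 3, 3, 0 (9 of 12) is removed, and someone with 1, 1, 1, 1 (4 of 12) is kept. Everyone who stops before week 4 is removed. T2-T3 has no requested number, so a retained participant can score 0 there.

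**2. How many are removed (assumed adherence).** Let each session be completed independently with probability p. The chance of at least one in a week is q = 1 − (1 − p)³, and the share removed is 1 − q⁴. The mean count is 12p in everyone and 12p/q in those retained.

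| p | q | removed | mean, all | mean, retained |
|---|---|---|---|---|
| 0.8 | 0.992 | 3% | 9.6 | 9.7 |
| 0.7 | 0.973 | 10% | 8.4 | 8.6 |
| 0.6 | 0.936 | 23% | 7.2 | 7.7 |
| 0.5 | 0.875 | 41% | 6.0 | 6.9 |

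If p varies between people (beta distribution, mean 0.7, concentration 4), 20% are removed and the mean rises from 8.4 to 9.4.

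**3. Arms that differ only in permanent stopping (assumed).** Let p = 0.8 in both arms, with weekly stopping of 3% v 10%. A retained participant was active in all four weeks, so the retained mean is 12p/q = 9.6/0.992 = 9.7 whatever the stopping rate.
- Stopping possible before any week-1 session: all-randomised means 8.9 v 7.4, difference 1.5. Retained means 9.7 v 9.7, difference 0.0. Removed: 14% v 36%.
- Stopping possible only from week 2: 9.2 v 8.3, difference 0.9. Retained difference 0.0. Removed: 12% v 29%.

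Appendix 1 invites participants to do the first exercise straight after the baseline questions, so the second version deserves at least equal weight.

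**4. Arms that differ in session completion, with no stopping (assumed).**
- Fixed p of 0.8 v 0.6: 9.6 − 7.2 = 2.4 in everyone; 9.68 − 7.69 = 1.99 in those retained.
- Mean p of 0.7 v 0.5 with the beta variation above: 8.4 − 6.0 = 2.4 in everyone; 9.4 − 8.2 = 1.2 in those retained.

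So the difference disappears in case 3 but only shrinks in case 4.

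**The case against.** The best counter-argument is about scope. The exclusion sentence directly follows the models for TMD, VAS, sleep and subscales, and no analysis of session count appears there. The next sentence allows the session count as a covariate in the same analyses, and a count cannot be its own covariate. This makes the narrower reading plausible. It does not settle the matter: the covariate is optional, and the T1-T2 count could sensibly be a covariate for T2-T3 use. On the narrower reading the plan simply gives no analysis population for outcome (b), so a clarifying sentence is needed either way.

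A reader might also infer stronger claims, which the documents do not support:
- *That a masked difference in use would lend false support to equivalence.* The hypothesis in section 3a covers mood, stress and sleep, and the primary objective covers TMD. Neither claims equivalent use.
- *That power to compare use is lost.* The plan names no between-arm test of session count, so there is no planned power to lose.
- *That any arm difference vanishes.* This holds only when arms differ solely in stopping before week 4. Stopping during week 4 after a session, or after T2, can still show.
- *That outcome (b) as a whole cannot fall below 4 of 12.* The floor applies to T1-T2 only.

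**Conclusion.** The point holds as a defect of wording with a real consequence if followed literally. That the T1-T2 count would be confined to 4 to 12, and that T2-T3 use would be taken from people selected on earlier use, needs no assumption beyond the literal reading. That use is overstated is likely rather than certain. Its size rests on assumed adherence: about 3% to 41% removed, and a rise in the mean from under 0.1 to about 1 session in the examples shown. An arm difference due to stopping before week 4 is hidden (0.9 or 1.5 sessions reduced to 0.0), while a difference in session completion is partly reduced (2.4 to 2.0 or 1.2). The point concerns a secondary outcome and an exploratory objective. It does not bear on the TMD comparison.

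**What to change.** In section 6:
1. State which analyses the weekly-session exclusion covers, and that it does not apply to outcome (b) or to use in weeks 4-8.
2. Report both counts by arm in all randomised participants from the Qualtrics log, scoring sessions not done as 0, including those after a participant stops.
3. Report by arm the number and share failing the one-session-per-week rule.

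In the same edit, give weeks 4-8 use one status, since section 3e calls it exploratory and section 6 secondary.

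The cost is a few sentences. No new data are needed, because sessions are already logged. The drawback for the authors is that reported mean use becomes somewhat less favourable.

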Sounds with a repetitive beat are traditionally used by Shamans to enter trance like states, and Tibetan monks also use sound when practicing meditation. Sound healing has been used by cultures across the world, for example, the Didgeridoo has been used by aboriginal tribes in Australia for over 40, 000 years [7]. Relaxation music played on “singing bowls” (Himalayan or Tibetan metal bowls or quartz crystal bowls) is readily available and is reported to have rapid, remarkable benefits on stress, mood and sleep. One clinical study in adults, using a pretest-post-test design, reported that an hour-long session of listening to metal and quartz crystal singing bowls resulted in an immediate mean 71% reduction in negative mood scores on the Profile of Mood States [16]. Another study used a randomised sequential crossover design to test the effect of adding either a 12 minute session of silence or listening to Himalayan singing bowls, prior to a 20 minute session of directed relaxation; the singing bowl intervention produced greater beneficial effects on physiological stress measures and mood [17]. In addition, another study reports that a single session of listening to Tibetan singing bowls led to greater physiological and psychological relaxation response (as shown by EEG and heart rate variability) compared with progressive muscle relaxation [18]. There is also preliminary evidence of the efficacy of Tibetan singing bowls in improving mood in young people; using a pre -test post-test design, one 25 minutes session of relaxation music played on quartz crystal singing bowls to a small group (n=11) of NZ adolescent males significantly reduced depression scores (on the Profile of Mood States) immediately after the session, as well as lowering tension scores [19].

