Taken together these findings suggest that relaxation music played on singing bowls may be beneficial in improving mood, decreasing stress, and improving sleep. Extending the previous work by co-PI [name] [19], this study seeks to compare the effects of listening to quartz crystal singing bowl music with guided relaxation on mood, stress and sleep in a larger sample of young adults. Participants will be randomly assigned to either the singing bowl (SB) or guided progressive muscle relaxation (PMR) condition. Participants will be asked to listen to singing bowl music or complete the PMR exercises for 10 minutes three time a week for four weeks (delivered online via the Qualtrics platform) and will then be given free access to the music or guided meditation for another four weeks whilst their use is monitored. Ratings of mood, stress and sleep will be completed at baseline, 4 weeks and 8 weeks. For one session per week, participants will be asked to complete visual analogue rating scales of their mood/stress immediately before and after the session to determine the acute effects of the intervention.

3. Study Design and Method

a) Hypothesis

Listening to singing bowl music will result in equivalent improvements in mood, stress and sleep compared with guided relaxation immediately after the session, and at 4- and 8-weeks post-intervention.

b) Design

Randomised controlled trial.

c) Intervention

Singing bowl music (SB)

The singing bowl relaxation music ('Tranquility' available on Spotify) was played by [name] and professionally recorded. The sound is produced by tapping the bowls and rubbing them with a rubber mallet. Each session took approximately 10 minutes.

Guided relaxation (PMR)

A guided progressive muscle relaxation audio (recorded by the NZ Cancer Society <https://www.youtube.com/watch?v=Zydrp3rfJdY>) and similar to the PMR script from the Anxiety and Phobia Workbook by Edmund Bourne [20]) was used. The session took approximately 12 minutes. Participants were instructed to start by sitting or lying comfortably, taking some deep breaths and then tense and relax muscles in a sequential manner from the head to the feet (see Appendix 6 for an example of the PMR script).

d) Outcome measures

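### The only power figure (>90%) is for detecting an effect on the secondary POMS subscales; none is given for the primary question, equivalence of singing bowls and PMR on TMD at 4 and 8 weeks

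*Combined protocol and SAP*

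**What the plan says.** Section 6, Sample size, contains the only power statement: "we are aiming to recruit a minimum of 100 participants (50 per group). This will provide > 90% power" at a two-sided alpha of 0.05, "to detect a medium size effect of the intervention on the POMS subscales".

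Section 3(d), Outcome measures, ranks the endpoints. "The primary outcome measure is the TMD", and for the subscales "we will conduct secondary analyses to examine the effects of the interventions on the subscale scores". Section 6 keeps this split, with TMD difference scores under primary outcomes and subscale difference scores under secondary outcomes.

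Section 3(e) gives the primary objective: "To determine if the effects of listening to singing bowl music are equivalent to that of progressive guided muscle relaxation", judged on TMD at 4 and 8 weeks. The hypothesis in section 3(a) is of the same kind: "Listening to singing bowl music will result in equivalent improvements in mood, stress and sleep compared with guided relaxation".

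The Analysis Plan in section 6 assigns repeated measures ANOVA to TMD and repeated measures MANOVA to the subscales. It removes from the analyses anyone who did not complete at least one session in each of the first four weeks. The supplied text gives no equivalence margin, no SD for TMD or its change, no rule for combining the two time points, and no allowance for exclusions or dropout.

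**The concern.** A power figure justifies a sample size only for the endpoint and question it was calculated for. Here both differ from the primary objective: subscales instead of TMD, and detecting an effect instead of showing that two active arms differ by no more than a tolerable amount. High power to detect a difference does not carry over to equivalence. Equivalence power depends on a margin, and the sample-size paragraph has none.

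The conclusion is what is at stake. The planned TMD analysis tests for a difference. If it is not significant, a reader may take that as evidence of equivalence from a trial with more than 90% power. The plan does not support that step.

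**Working it through.** **Inputs from the protocol.** 50 per group; two-sided alpha 0.05; power above 90%; a medium effect with no number, test, contrast or correlation (section 6, Sample size).

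**Inputs assumed.** Medium taken as d = 0.5 (or f = 0.25 for repeated measures ANOVA); margins of 0.4 to 0.7 SD of TMD change; true SB-PMR difference 0; correlation of 0.5 to 0.7 between the 4- and 8-week changes; 40 per group as an example of what the adherence exclusion might leave.

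**1. The plan's own figure.** It can be reproduced on some readings and not on others.

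- Within-arm paired t test, d = 0.5, n = 50: noncentrality 0.5 × √50 = 3.54 on 49 df, power 93.4%.
- Between-arm t test on change, d = 0.5 of the change SD, 50 per group: noncentrality 0.5 × √(50/2) = 2.5 on 98 df, power 69.7%.
- Group-by-time ANOVA, f = 0.25, N = 100, two time points. With f defined on the raw-score SD and correlation 0, λ = 0.25² × 100 × 2 = 12.5 and power is 93.8%, rising with the correlation. On this definition the effect is a between-arm difference in change of 1.0 raw-score SD. With f taken from partial eta-squared, λ = 0.25² × 100 = 6.25 and power is about 70%.

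The within-arm reading fits the cited data best, since those data are reductions after sessions. The Background introduces the main singing bowl source in these words: "One clinical study in adults, using a pretest-post-test design, reported that an hour-long session".

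**2. What the planning data supply.** The sample-size paragraph cites subscale reductions of 0.49 to 1.23 (SD 0.19 to 1.05) after singing bowls (n = 62), a significant fall in depression scores in teenage males (n = 11), and subscale differences of 2.13 to 4.25 (SD 2.38 to 4.47) after PMR or autogenic relaxation (n = 8). It gives no TMD mean or SD and no SB-PMR difference.

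**3. Equivalence on TMD, one time point.** Two one-sided tests (TOST) on the difference in change, in SD units. SE = √(2/50) = 0.20. The normal approximation is

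power = 2Φ(margin/SE − z₁₋α) − 1.

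At a margin of 0.5 and one-sided 0.05: 2Φ(2.5 − 1.645) − 1 = 2Φ(0.855) − 1 = 61%. The exact result, averaging over the distribution of the pooled SD on 98 df, is 59.8%. Exact results for 50 per group:

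| Margin (SD of TMD change) | One-sided 0.05 | One-sided 0.025 |
|---|---|---|
| 0.4 | 27% | not tabulated |
| 0.5 | 60% | 39% |
| 0.6 | 82% | 69% |
| 0.7 | 93% | 87% |

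Power of 90% needs a margin of about 0.66 SD at one-sided 0.05, or 0.73 SD at one-sided 0.025.

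**4. Fewer analysed.** With 40 per group, SE = √(2/40) = 0.224. At a 0.5 SD margin and one-sided 0.05 the approximation is 2Φ(2.236 − 1.645) − 1 = 45%; the exact result is 43%.

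**5. Both time points must pass.** This was simulated with bivariate normal mean differences and a pooled covariance matrix on 98 df. At 50 per group, a 0.5 SD margin and one-sided 0.05, power is 39%, 41% and 43% at correlations of 0.5, 0.6 and 0.7.

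**The case against.** A fair defence has four parts.

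- **The figure may be correct for its own target.** This stands. The within-arm reading gives 93%, and the raw-score ANOVA reading also exceeds 90%. A reader who sees the 70% for a between-arm difference of 0.5 SD might infer that the stated figure is wrong. The protocol does not support that, because it names neither the test nor the effect metric.
- **TMD is built from the subscales, so power on them is not irrelevant.** This is true of the construction, since section 3(d) defines TMD as a signed sum of subscale totals. It does not turn power to detect an effect into power to show equivalence, and no SD for the sum is given.
- **Equivalence may be loose wording.** The word appears in both the hypothesis and the primary objective. Even if a difference test were meant, the figure would still concern secondary endpoints and TMD would have no power statement.
- **The more basic gap is the missing margin and equivalence test.** This is right, and it shapes the remedy: rewriting the power sentence alone would size the trial for a test that the Analysis Plan does not run. The mismatch is still a separate fault, because adding a margin elsewhere would leave the subscale figure as the only justification for 100.

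A reader might also infer that 100 is too few. That does not follow. The margins are assumed, power passes 90% at a 0.7 SD margin for one time point at one-sided 0.05, and 100 is a stated minimum, so more may be enrolled.

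**Conclusion.** The concern holds as a mismatch. The >90% figure used to justify 50 per group addresses detection of an effect on secondary subscales, and no power is stated for equivalence of SB and PMR on TMD at 4 and 8 weeks. It should be fixed, because the figure could otherwise be used to read a non-significant TMD difference as equivalence.

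The size cannot be fixed from the documents. Over the assumed margins of 0.4 to 0.7 SD, equivalence power at one time point runs from about 27% to 93%. At 0.5 SD, where it is 60%, it drops to about 43% with 40 per group, or to 39-43% if both time points must pass with 50 per group. All of these assume a true difference of exactly zero and one-sided 0.05. A true difference of 0.1 SD would lower the 60% to 54%. The adequacy of 50 per group turns on inputs that the sample-size paragraph omits.

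**What to change.** Replace the power sentence with one for the primary question, for example: with [n] per group expected after the adherence exclusion, an SD of TMD change of [s, with source] and a true SB-PMR difference of [d], the trial has [x]% power to show equivalence within ±[margin, with justification] at [4 weeks / 8 weeks / both], using two one-sided tests at one-sided alpha [a] or the matching confidence interval. The sponsor sets the margin, alpha and time-point rule.

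Put the same three items in the Analysis Plan. State there that equivalence is concluded only if the confidence interval for the SB-PMR difference in TMD change lies wholly within the margin, and never from a non-significant ANOVA. If the resulting power is low, say so and limit the equivalence conclusion accordingly. Keep the subscale figure only if it is labelled secondary and its test, contrast and effect metric are given.

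**Cost.** One paragraph rewritten, a matching addition to the Analysis Plan, and no change in enrolment. The sponsor must choose and defend a margin and find an SD for TMD change, which the protocol does not supply. The stated power may look less favourable.
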